### 5.7 Selection of Investigational Products

Selection of interventions will be done by the Therapeutic Evaluation Committee (TEC) based on evidence supporting the intended mechanism of action, target engagement, previous pre-clinical data and Phase I or other clinical data (including safety data available for each intervention), and compatibility with the Master Protocol Study Design (see Section 5.3). During the trial, a therapeutic product may be discontinued early due to safety concerns.

### 5.8 Planned Number of Sites

Research participants will be enrolled from approximately 30 PPMI sites in the US.

### 5.9 Treatment Duration

Treatment duration for placebo-controlled interventions will be minimum 24 months for each intervention. All participants may remain on the originally assigned treatment arm until the last randomized participant has the opportunity to complete 24 months of follow-up for that specific RSSP or until 24 months since randomization have passed (if terminated early). The RSSP will be closed once all participants have completed the follow-up period. Post-treatment follow-up duration for each intervention will be described in the RSSPs. All participants will be encouraged to continue follow up in the PPMI clinical observational study as per PPMI Schedule of Activities (SOA).

# 6. TRIAL OBJECTIVES AND ENDPOINTS

In this trial, multiple investigational products for NSD Stage 2B will be tested simultaneously or sequentially. The Master Protocol objective is to assess the impact of putative NSD therapies in participants with Early Stage NSD on Dopamine Transporter Single-photon emission computed Tomography (DAT SPECT) imaging, a clinical measure of symptom worsening, feasibility, safety, and tolerability. Additional analyses may examine many other exploratory clinical outcome measures and biomarkers.

### 6.1 Multiple Primary Endpoints

- 1. DAT SPECT imaging as measured by the rate of progression in the mean striatum Specific Binding Ratio (SBR) from baseline through follow-up.
- 2. Clinical outcome as defined by the rate of progression in the Movement Disorder Society-Sponsored Revision of the Unified Parkinson's Disease Rating Scale (MDS-UPDRS) Part III score from baseline through follow-up or the initiation of dopaminergic treatment.

## 6.2 Secondary Endpoints

- 1. Feasibility as defined by ability to recruit, retain participants, and complete RSSP study activities as per schedule of activities.
- 2. Safety as measured by all treatment-emergent adverse events (TEAEs), and serious adverse events (SAEs) for the active treatment arm versus placebo in each RSSP.
- 3. Tolerability as measured by ability to complete an RSSP on the assigned dose and treatment arm (active versus placebo).

## 6.3 Key Exploratory Endpoints

- 1. The number of participants who progress from NSD stage 2B to NSD Stage 3 or higher
- 2. Clinical outcome as defined by the rate of progression in the MDS-UPDRS Total score from baseline through follow-up or the initiation of dopaminergic treatment and rate of progression in Part I & II subscores from baseline through follow-up.
- 3. Change in cognition as defined by the number of participants developing new syndromes of mild cognitive impairment (MCI) or dementia.
- 4. Change in functional status as measured by Penn Parkinson's Daily Activities Questionnaire-27 (PDAQ-27) from baseline through follow-up.
- 5. Time to progression milestones as defined by Brumm et  $al^1$ .

## 6.4 Other Exploratory Endpoints

A range of additional exploratory clinical, pharmacokinetic, and biomarker variables as per PPMI protocol will also be assessed, including but not limited to:

- 1. Clinical Measures
  - a. The number of participants developing clinically defined syndromes including PD, DLB, or Multiple System Atrophy (MSA) as per established diagnostic criteria as determined by the SI clinical judgement.

- b. Change in the clinical diagnosis as determined by the SI or treating physician
- c. Change from baseline in the PPMI neuropsychological cognitive battery
- d. Change in neuropsychiatric domain including measures of depression and anxiety
- e. Change from baseline in digital outcome measures of function, activity, sleep, and cognitive.
- f. Change from baseline in Scales for Outcome in Parkinson's Disease-Autonomic (SCOPA-AUT) and other autonomic measures
- g. Change from baseline in Quality of Life (Neuro-QoL)
- h. Change from baseline in 11-item PD symptom screening questionnaire (Brief Motor Screen)
- i. Change from baseline in the global disability scale Participant Global Impression (PGI-S) and Clinical Global Impression (CGI-S)
- j. Change from baseline in the novel Participant Reported Outcomes (PRO)
- 2. Pharmacokinetic Measures
  - a. Pharmacokinetic parameters of the intervention as defined in each RSSP.
  - b. Correlation between drug exposure and safety/efficacy outcome measures as defined in each RSSP
- 3. Pharmacodynamic Measures
  - a. Biomarkers of target engagement based on intervention profile as defined in each RSSP.
  - b. An array of imaging including molecular imaging and Magnetic Resonance Imaging (MRI), biofluids, and tissue biomarkers of disease progression and state may be included based on the PPMI panel inclusive but not limited to:
    - MRI imaging (structural and advanced imaging sequences as per PPMI protocol)
    - Biomarkers of n-asyn pathology (plasma, CSF, skin, potentially other tissue)
    - Plasma, CSF Amyloid, tau, ptau, and Amyloid/Tau Positron emission tomography (PET) imaging depending on the profile of the intervention)
    - Inflammatory biomarkers
    - Neurodegeneration (Neurofilament light chain)
    - Genotyping

# 7. INCLUSION/EXCLUSION CRITERIA

### 7.1 Inclusion Criteria

Participants will be eligible for inclusion in this Master Protocol if they meet the following criteria:

- 1. Enrollment in PPMI observational study
- 2. Able to provide informed consent.
- 3. Diagnosis of NSD Stage 2B (see Table 3)
- 4. Female participants of childbearing potential and male participants must agree to use contraception as detailed in the RSSP.
- 5. Age 60 years or older at Screening visit.

6. Meet any additional inclusion criteria accessible at the time of screening (if applicable) for at least one active RSSP

### 7.2 Exclusion Criteria

Participants fulfilling any of the following criteria are not eligible for inclusion in this Master Protocol, or able to participate in an RSSP:

- 1. Received any of the drugs associated with symptomatic parkinsonism within 6 months of Randomization Visit (see Appendix 2).
- 2. Received dopaminergic therapy (levodopa or dopamine agonist) for NSD motor syndrome or cholinesterase inhibitors for NSD cognitive syndrome within 90 days prior to or at the time of randomization.
- 3. Any other medical or psychiatric condition or lab abnormality, which in the opinion of the site investigator might preclude Master Protocol participation.
- 4. Individuals taking any of the drugs that might interfere with the DaTscan read out unless they are willing and medically able to hold the medication for at least 5 half-lives before DAT SPECT imaging (see Appendix 1).
- 5. Women may not be pregnant, lactating or planning pregnancy during the Master Protocol.
- 6. Participation in other investigational drug studies less than 30 days prior to screening (unless specified otherwise in the RSSP).
- 7. History or current diagnosis of electrocardiogram (ECG) or cardiac abnormalities indicating significant risk of safety for participants such as:
  - a. Myocardial infarction, unstable angina pectoris, transient ischemic attack, stent placement or coronary artery bypass graft, any of those within 6 months of screening.
  - b. Cardiac failure [New York Heart Association (NYHA) functional class II-IV], stroke or clinically significant uncontrolled arterial hypertension.
  - c. Clinically significant cardiac arrhythmias (e.g., ventricular tachycardia), complete bundle branch block, high-grade AV block (e.g., bifascicular block, Mobitz type II- and third-degree AV block).
  - d. Resting QTcF >450 ms (in males) or >460 ms (in females) and < 300 ms (regardless of sex) at screening or inability to determine the QTcF interval.
  - e. Long QT syndrome, family history of idiopathic sudden death or congenital long QT syndrome.
- 8. Score "yes" on item 4 or item 5 of the Suicidal Ideation section of the C-SSRS, if this ideation occurred in the past 6 months, or "yes" on any item of the Suicidal Behavior section if this behavior occurred in the past 2 years, except for the "Non-Suicidal-Self Injurious Behavior" (item also included in the Suicidal Behavior section).
- 9. Study participant has a current history of alcohol or drug use disorder, as defined in the Diagnostic and Statistical Manual of Mental Disorders: DSM-5-TR, within the previous 5 years before screening.
- 10. Clinically significant abnormalities in laboratory test results at the screening visit, including hepatic and renal panels, complete blood count, chemistry panel and urinalysis as determined by SI.

- 11. Presence of human immunodeficiency virus (HIV) infection based on either history or testing.
- 12. Any of the following:
  - a. Presence of hepatitis B surface antigen or positive HBV DNA at Screening
  - b. Positive hepatitis C antibody test result at Screening or within 3 months prior to starting study drug. NOTE: Participants with positive hepatitis C antibody due to prior resolved disease can be enrolled if a confirmatory negative hepatitis C ribonucleic acid (RNA) test is obtained. Where hepatitis C RNA testing is unavailable, a positive hepatitis C antibody test will lead to exclusion.

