## 9.1 Master Protocol Screening Visit

Screening evaluations will occur within 90 days prior to the baseline visit. Screening has been separated into two groups depending on their last PPMI visit and is further defined in the schedule of assessment table. Before any of the screening evaluations are performed for the specific purpose of this Master Protocol, the participant must provide informed consent for this Master Protocol in compliance with Good Clinical Practice (GCP) and IRB requirements. Collection of AE data will begin after the informed consent is signed and will continue until the participant completes their assigned RSSP, 30 days after treatment discontinuation (whichever comes first), or per the defined terms in the RSSP. The screening procedures listed below will be performed and documented to assess whether a participant meets inclusion/exclusion criteria. Scope of activities at the screening visit will depend on the time of the visit in relation to the last PPMI annual visit.

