### 9.2 Baseline/Randomization Visit

The Baseline/Randomization Visit will take place in-person after the Master Protocol Screening Visit. The following procedures will be performed and are listed in the order to be completed:

- Confirm Master Protocol inclusion/exclusion eligibility
- Measure Weight
- Measure Vital signs and Orthostatic Blood Pressure
- Administer Neurological and Motor Assessments including: MDS-UPDRS Part III and Hoehn & Yahr.
- Perform Global Function Assessments including: CGI-S, PGI-S, Novel PRO, PDAQ-27
- Administer the C-SSRS Baseline questionnaire
- Collect research samples (urine and blood)

- Review and document concomitant medications
- Assess any accessible inclusion/ exclusion criteria for eligibility into all available RSSPs. This is done via available data obtained or collected in the Master Protocol Screening visit.
- Randomization to active study drug or placebo
- Assess and document AEs related to Master Protocol procedures
- Assess current medical conditions
- Assess pregnancy status

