## 9.4 Month 1 Visit

This visit will take place in person approximately  $28 \pm 7$  days after the Baseline Visit. The following procedures will be performed:

- Measure Weight, Vital Signs & Orthostatic Blood Pressure
- Administer MDS-UPDRS Part I-III
- Digital Assessment per the PPMI Digital Sub Study (as needed)
- Collect blood samples for clinical safety labs
- Perform 12-lead electrocardiogram
- Administer C-SSRS Since Last Visit Short Form
- Concomitant medication review
- LEDD Medication Initiation Log (as needed)
- Assess and document AEs
- Current Medical Conditions Review
- Report of pregnancy (as needed)
- Surgery for PD (as needed)

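### Exclusion 7d joins its upper and lower QTcF limits with *and*, so read literally no measured QTcF excludes a woman and no value below 300 ms excludes anyone

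*Protocol*

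**What the plan says.** Section 7.2 of the Protocol lists exclusions, any one of which makes a person ineligible. Exclusion 7 covers ECG and cardiac abnormalities. Its item (d) gives the QTcF rule as "Resting QTcF >450 ms (in males) or >460 ms (in females) and < 300 ms (regardless of sex) at screening", and continues "or inability to determine the QTcF interval". The main exclusion criteria in the synopsis (Section 4) carry the same wording. Nowhere else does the Master Protocol restate the limits.

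Three neighbouring provisions also bear on a participant with an abnormal QTcF:

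- The stem of exclusion 7 introduces its items as examples, with "cardiac abnormalities indicating significant risk of safety for participants such as".
- Item 7e lists "Long QT syndrome, family history of idiopathic sudden death or congenital long QT syndrome".
- Exclusion 3 allows exclusion for any other condition or laboratory abnormality "which in the opinion of the site investigator might preclude Master Protocol participation".

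The criterion is judged on the screening ECG. Section 9.1 says: "Screening evaluations will occur within 90 days prior to the baseline visit". Section 9.2 opens its Baseline list with "The following procedures will be performed and are listed in the order to be completed", and that list contains no ECG. The next scheduled ECG is at Month 1, where Section 9.4 has "Perform 12-lead electrocardiogram".

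**The concern.** The sentence in 7d has three numeric limits and one limb for an interval that cannot be determined. Every join is *or* except the one between the upper limits and the lower limit, which is *and*. Because this is an exclusion rule, *and* requires both conditions to hold in the same person, and a single QTcF cannot be above 460 ms and below 300 ms.

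Item 7d holds the only numeric QTcF limits in the Master Protocol. The Amendment 1 summary of changes explains that these exclusions were moved into the Master Protocol so that each RSSP need not carry them separately, so an error here passes to every regimen on the platform. Section 16.5.3 makes each site investigator responsible for enrolling only people who meet all the criteria. A rule that has to be silently corrected before it can be applied invites different decisions at different sites, and argument afterwards about whether an enrolment was a deviation. A checklist or electronic check transcribed word for word would carry the fault.

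**Working it through.** The protocol gives no figure to reproduce, so the check is a logical one.

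**Inputs** (Section 7.2, item 7d, identical in the synopsis): upper limit for men, above 450 ms; upper limit for women, above 460 ms; lower limit for either sex, below 300 ms; undeterminable QTcF joined by *or*.

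**Readings of the numeric part:**

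- A, *and* binds before *or*: (man and QTcF > 450) or (woman and QTcF > 460 and QTcF < 300).
- B, *and* applies to both upper limits: [(man and QTcF > 450) or (woman and QTcF > 460)] and QTcF < 300.
- C, evident intent: (man and QTcF > 450) or (woman and QTcF > 460) or QTcF < 300.

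Each reading was evaluated at every whole millisecond from 200 to 700 ms, by sex:

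| Reading | Men excluded at | Women excluded at |
|---|---|---|
| A | 451–700 ms (250 values) | none (0 values) |
| B | none (0 values) | none (0 values) |
| C | 200–299 and 451–700 ms (100 + 250 = 350 values) | 200–299 and 461–700 ms (100 + 240 = 340 values) |

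Under A, one of three numeric limits works (men above 450 ms) and two are void. Under B, all three are void. Both literal readings therefore agree that no measured QTcF excludes a woman and that no QTcF below 300 ms excludes anyone. They differ only on men above 450 ms. An undeterminable QTcF excludes either sex in every reading.

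**Context from the visit schedule.** Screening may fall 1 to 90 days before baseline, and Month 1 is 28 ± 7 days after it. The interval between the screening ECG and the next scheduled one is at most 90 + 28 + 7 = 125 days and at least 1 + 28 − 7 = 22 days. This interval would be the same if 7d were worded correctly, so it does not measure the effect of the error. It shows only that the screening ECG is the one scheduled opportunity to apply a numeric QTcF limit before treatment starts.

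**The case against.** The strongest reply is that clinical prose is not Boolean code. The qualifier that the lower limit applies to both sexes makes no sense inside a clause about women, so a clinician will take *and* as adding a further excluded range. The protocol uses *and* to list groups elsewhere: inclusion 4 joins women of childbearing potential and men in this way, and nobody takes it to mean one person who is both. That argument is sound as to intent, and few cardiology-literate readers would be misled. It does not make the sentence correct. An operative exclusion limit should not depend on the reader repairing it, and no other section states it properly.

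A second reply is that the person is not left unprotected. The stem of exclusion 7 offers its items as examples, 7e covers long QT syndrome and family history, and exclusion 3 leaves room for the site investigator's opinion. A woman with a markedly prolonged QTcF could be excluded by these routes. This also stands, and it is why the finding is confined to 7d itself. But these routes rest on diagnosis, history or judgement. A woman only just above 460 ms has no numeric rule applied to her.

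Third, no practical effect is shown. No checklist applying 7d literally is in the documents, and an RSSP may add its own criteria or ECGs; none was available. That is accepted, and it limits the weight of the point without removing the error.

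**Conclusion.** The concern holds. As written, 7d and its synopsis copy exclude no woman on a measured QTcF and nobody below 300 ms, under either literal grouping. Two of three numeric limits are void on the more natural grouping and all three on the other. The conclusion rests only on the wording of the two current passages and on the fact that no value is both above 460 ms (or 450 ms) and below 300 ms.

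The weight is modest. The intent is plain, partial safeguards exist, and how many participants could be affected cannot be worked out from the protocol. It remains a drafting error in a cardiac safety threshold and should be corrected. The statistical design is untouched.

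**What to change.** In Section 7.2 (7d) and in the matching synopsis bullet, write the rule as alternatives, each sufficient alone: resting QTcF at screening > 450 ms (males), **or** > 460 ms (females), **or** < 300 ms (either sex), **or** QTcF not determinable. Leave the limits themselves unchanged. Confirm that any eligibility checklist or electronic check already in use applies them in this way.

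The cost is a wording change in two places. Section 16.5.1 requires an amendment and central IRB approval for any change to the Master Protocol, so the correction can travel with the next amendment. Sample size, randomization and analysis need no change.

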## 8. PARTICIPANT SELECTION AND ENROLLMENT

## 8.1 Identifying Participants

This Master Protocol will be initially conducted at selected PPMI qualified centers in the US and participants must be enrolled in the PPMI Clinical study. Potential eligibility for P2P Master Protocol will be determined based on the potential to meet Mater Protocol inclusion/ exclusion criteria and assessed centrally for consideration for further contact. Sites participating in this Master Protocol will be notified of potentially eligible PPMI participants enrolled at their site to be contacted for Master Protocol screening. Information about all research participants enrolled into the trial will be recorded in the Electronic Data Capture (EDC) system.

#### 8.1.1 Ineligible Participants

All consented participants from the PPMI study will be screened for eligibility for P2P based on the Master Protocol inclusion/exclusion criteria. For participants who were deemed potentially eligible for the Master Protocol but did not qualify on further screening, the reason for ineligibility for the Master Protocol will be tracked. Similarly, participant ineligibility for any individual RSSP will also be documented.

### 8.2 Randomization

#### 8.2.1 Randomization Procedures

Randomization will be conducted using an interactive response technology (IRT) system embedded within the EDC. The randomization for the Master Protocol consists of a two-stage tiered randomization as described below (see Figure 1).

- 1. In the first stage, participants will initially be assessed according to the Master Protocol inclusion and exclusion criteria. All eligible participants will then be assessed for any additional RSSP specific inclusion and exclusion criteria above that for the Master Protocol that are accessible at the time of screening. Assuming a research participant qualifies for one or more of the ongoing RSSPs, the participant will be randomized equally among all *J* actively enrolling regimens for which they are eligible. Here, regimen denotes both active treatment and placebo groups.
- 2. In the second stage, once assigned to a regimen the participant will then provide informed consent for that specific regimen at their scheduled Regimen-Specific Screening visit. If all additional regimen specific eligibility criteria are met, participants will be stratified by

their baseline MDS-UPDRS part III score ( $<7 \text{ vs.} \ge 7$ ) and randomized in a *J*:1 manner via the IRT system to either the active treatment or placebo for the sub protocol. If the participant screen fails for the assigned regimen (prior to randomization within the regimen), they can be re-randomized to one of the other actively enrolling regimens and complete the required screening procedures. Eligible participants who choose not to consent to their assigned regimen will not be given the opportunity to be re-randomized into an alternative regimen.

The objective of the randomization scheme is to have approximately 1:1 randomization for each active treatment versus concurrently randomized controls.

#### 8.2.2 Blinding

In this trial, investigational products may have a different mode (e.g., oral, subcutaneous, intravenous) or frequency of administration and may be introduced at different time points. Each regimen will have its own concurrent, randomized placebo control arm.

Research participants, SIs, and everyone involved in the conduct of the Master Protocol, will not be blinded to the regimen assignments but will be blinded to the randomized treatment assignments within an RSSP. The randomized treatment assigned for participants in that sub-protocol will be kept secure and will only be accessed according to the Unblinded Personnel List and Procedures and the Emergency Unblinding Plan.

#### 8.2.3 Emergency Unblinding

In the event of a medical emergency that necessitates the unblinding of the Independent Medical Monitor (IMM) or a SI to assure safety for a participant, emergency unblinding of that single participant may be undertaken as outlined in the medical monitoring plan. Emergency unblinding for a research participant will only be undertaken when it is essential to treat the participant safely. It must only be used in an emergency when the identity of the treatment arm must be known to the SI to provide appropriate medical treatment or otherwise ensure the safety of research participants or others exposed to investigational products. In most cases, investigational product discontinuation and knowledge of the possible treatment assignments will be sufficient to treat a study participant who presents with an emergency condition. However, if unblinding is necessary, the blind may be broken only for that participant. In that case the participant will be terminated from the RSSP but can remain in the Master Protocol following the procedures as outlined in Section 8.4.

